### **8.3.3 Vital Signs**

Vital signs are composed of systolic/diastolic blood pressure, respiratory rate, heart rate, and body temperature. Summary statistics for baseline, each post-baseline measurement, and change from baseline for each post-baseline measurement will be presented for each treatment arm and overall, by each vital sign parameter.

Baseline is defined as the pre dose observation value of each dosing visit.

Also all vital sign values will be listed in data listings.

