**Figure 1 CMB305 or Matching Placebo Dosing Regimen**

LV305 or matching placebo is administered as 4 separate 1-mL SC on Days 1, 22, 50, and 78, each preferably administered in a separate upper or lower limb (or stump if the subject has had a resection), or administered at least 3 cm from the neighboring injection site if on the same limb/stump.

G305 or matching placebo is administered IM on Days 36, 64, and 92, and then at 8-week intervals up to 1 year or until investigator-determined PD (using RECIST v1.1) is documented or unacceptable toxicity, whichever occurs first..

Three placebos (fully matched to characteristics of LV305, the NY-ESO-1 protein, and GLA-SE) will be provided for this study and will be administered on the same schedule and by the same route as the corresponding experimental therapy components to ensure that the sponsor, site personnel (including pharmacist), and subjects remain blinded to study drug for the duration of the study.

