### 5.2.3 Vital Signs

Vital Signs include body temperature, heart rate, respiratory rate, and resting systolic and diastolic blood pressure. On the day of each dosing, vital signs will be obtained before dosing and 30 minutes after dosing ( $\pm 10$  minute window). Blood pressure and heart rate will be measured no more than 60 minutes before the scheduled dosing.

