## 8.3 Safety Analyses

All analyses for the safety evaluation variables will be performed on safety set by treatment arm and overall.

Baseline is defined as the last non-missing value prior to the first dose date on day 1, unless otherwise noted.

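### The vital-sign change from baseline in SAP 8.3.3 captures only the acute same-visit change; no within-subject change from before treatment is planned

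*SAP*

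**What the plan says.** SAP 8.3 gives a default baseline for safety variables, with room for exceptions: "Baseline is defined as the last non-missing value prior to the first dose date on day 1, unless otherwise noted". SAP 8.3.2 (laboratory) and 8.3.4 (ECG) present change from baseline without a definition of their own, so the default governs them.

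SAP 8.3.3 makes an exception for vital signs: "Baseline is defined as the pre dose observation value of each dosing visit". It plans three by-arm summaries: "Summary statistics for baseline, each post-baseline measurement, and change from baseline for each post-baseline measurement will be presented for each treatment arm and overall". It also lists all values by subject. No other vital-sign change is specified in the SAP, and Protocol 7.8 adds none.

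On timing, SAP 5.2.3 says: "On the day of each dosing, vital signs will be obtained before dosing and 30 minutes after dosing". SAP Figure 1 gives the dosing days: "LV305 or matching placebo is administered as 4 separate 1-mL SC on Days 1, 22, 50, and 78", and "G305 or matching placebo is administered IM on Days 36, 64, and 92, and then at 8-week intervals up to 1 year". The notes to Table 2 put the first boost after Day 92 on Day 148. Table 2 marks vital signs at every Prime Phase visit and at the Boost visits, and at none in the Post-treatment or Long-term Follow-up periods.

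**The concern.** Vital signs are a named safety assessment in the Protocol synopsis and a safety endpoint in SAP 5.2.3, and dosing is repeated for up to a year. Two questions arise. Does an injection produce an acute reaction within the half hour? Does repeated vaccination move blood pressure, heart rate or another sign away from where the subject started? The same-visit baseline answers the first question only. Because the baseline is reset at each visit, a subject whose resting value has moved since Day 1 carries that movement in both terms of the subtraction. What would be missing is the ordinary within-subject contrast with the pre-treatment value, by visit and by arm, which the SAP keeps for laboratory and ECG variables.

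**Working it through.** The documents give no figure to reproduce here, so the check is on the definition and the visit calendar.

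**Step 1. Dosing calendar.** LV305 or placebo: Days 1, 22, 50, 78. G305 or placebo: Days 36, 64, 92, then Day 148 and every 56 days: 204, 260, 316. The next would be 316 + 56 = 372, which is past one year. The combined calendar is 1, 22, 36, 50, 64, 78, 92, 148, 204, 260, 316, or 11 visits.

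**Step 2. Vital-sign calendar.** In Table 2 the Prime Phase vital-sign visits are Days 1, 22, 36, 50, 64, 78 and 92. All seven are dosing days, and the Boost visits are dosing visits too. After Screening, then, no scheduled vital-sign visit falls outside dosing.

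**Step 3. What the change becomes.** At visit k, let pre(k) and post(k) be the pre-dose and 30-minute readings. Suppose a sustained shift S is present from Day 22 on, and each dose has an acute effect A:

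- pre(k) = pre(1) + S
- post(k) = pre(k) + A

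Under SAP 8.3.3 the change is post(k) − pre(k) = A, and S drops out.

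Under SAP 8.3, with the Day 1 pre-dose value as baseline, the change is pre(k) − pre(1) = S before the dose and post(k) − pre(1) = S + A after it.

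**Step 4. Illustration.** The level of 120 and the values of S and A are assumptions, not document figures.

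| S | A | Change under 8.3.3 | Pre-dose change under 8.3 | Post-dose change under 8.3 | Pre-dose value at the visit |
|---|---|---|---|---|---|
| 5 | 0 | 0 | 5 | 5 | 125 |
| 5 | 3 | 3 | 5 | 8 | 125 |
| 10 | 0 | 0 | 10 | 10 | 130 |
| 10 | 3 | 3 | 10 | 13 | 130 |
| 20 | 0 | 0 | 20 | 20 | 140 |
| 20 | 3 | 3 | 20 | 23 | 140 |

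The third column depends on A alone. The last column shows where the shift remains visible: the absolute value at each visit, which SAP 8.3.3 also summarises.

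**Step 5. A side gap.** Protocol 5.6.2 provides for delayed doses. If vital signs are taken at a visit where the dose is withheld, there is no pre-dose value, and 8.3.3 defines no baseline for that reading.

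**The case against.** Four points can be made for the plan as written.

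- *The exception is permitted and has a purpose.* SAP 8.3 allows other definitions, and paired readings around an injection call for a same-visit reference when the interest is acute reaction. This stands. The two sections do not contradict each other, and the same-visit change is worth keeping.
- *The shift is not hidden.* A reader might infer that a sustained shift would be reported as zero throughout the vital-sign output. The documents do not support that. On the literal reading each visit's pre-dose value is a baseline and is summarised by arm, as are the post-dose values, and every reading is listed. With a randomised placebo arm, a treatment-related drift would appear as a difference between arms in the visit means. This stands too, and it limits the point to the change summary. What those outputs do not give is each subject's change from his or her own starting value.
- *Adverse events offer another route.* Protocol 6.4.7 includes vital signs in the medical review behind safety assessment, and Protocol 7.8 rests safety primarily on reported adverse events. This stands for clinically evident changes. It does not replace a summary of the measurements, since a moderate average shift need not be recorded as an event.
- *Nothing decisive turns on it.* The table is descriptive, no data are lost, and the contrast could be produced later. This is correct and sets the weight of the point.

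A reader might also argue that by-visit means are unusable because dosing stops at progression, and use the planned PFS to size the loss. That does not hold either: Protocol 6.5.2 lets subjects continue study drug after RECIST progression under stated conditions, so the progression-free proportion is not the proportion still dosed. The proposed change table would also cover only subjects attending each visit; its gain is the pairing with their own pre-treatment value.

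**Conclusion.** The point holds as a minor improvement to the safety analysis. As defined, the vital-sign change from baseline measures only the acute same-visit change at each of the 11 scheduled dosing visits. A sustained within-subject shift from before treatment cancels out of that one summary, whatever its size, and can be seen only indirectly in visit-level values, listings or adverse event reports.

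This rests on the literal wording of SAP 8.3.3 and on the scheduled visits. Table shells are in separate files (SAP section 11), so their layout could not be checked. The numbers in the illustration are assumed and show only the cancellation. Alpha, power, sample size and event counts are untouched.

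**What to change.** In SAP 8.3.3:

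1. For change from baseline by visit, use the SAP 8.3 baseline, and say explicitly that the Day 1 pre-dose reading counts. The SAP 8.3 wording refers to the first dose date, so without this a programmer could exclude a same-day reading and fall back to Screening.
2. Keep the same-visit pre-dose value as the reference for a separate summary, labelled as the change from pre-dose to 30 minutes post-dose.

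The first change also supplies a baseline for readings at visits where the dose is withheld. The cost is a short wording change before database lock and one more descriptive table, with no new data collection.

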### **8.3.4 ECG**

ECG absolute individual parameters and the change from baseline will be summarized by treatment arm and overall per assessment as continuous measurements.

QTc and maximum QTc (including changes from baseline) will be summarized as both continuous and categorical measurements, where the categorical for QTc, and change from baseline QTc are as follows, respectively:

- Observed post baseline value: >450-≤480; >480-≤500 and >500 (msec)
- Change from baseline: >30-≤60 and >60 (msec)

All ECG measurements will be presented in data listings.

### **8.3.5 Physical Findings**

Physical examination results will be presented in a listing, including screening and each post treatment visit.

### **8.3.6 Dosing and Extent of Exposure**

Treatment exposure will be provided by treatment arm. The number of CMB305 or placebo injections, duration of exposure, and number of subjects with dose reductions/interruptions will be summarized by treatment arm based on the Safety set.

### **Dosing and Extent of Exposure**

The duration of exposure is defined as the total number of days on the planned study treatment, temporary treatment discontinuation and planned treatment misses will be ignored.

The following algorithm will be used to calculate the duration of study treatment exposure for subjects who took at least one dose of study treatment:

Duration of exposure (days) = [(date of last administration of study treatment) – (date of first administration of study treatment) + 1]

### **8.3.7 Prior and Concomitant Medications**

All concomitant medications and prior medications will be coded to therapeutic drug classes and generic drug names using the World Health Organization (WHO) Drug Classification. The incidence of prior and concomitant medication usage will be summarized by treatment arm, by therapeutic drug class, and generic drug names on safety set separately.

**Concomitant medication** is any medication with start date on or after the initial dosing of study treatment.

**Prior medication** is defined as any medication with start date on or before the first day of study treatment, or medication with start date missing.

Each subject will be counted once only for each therapeutic drug class, generic drug names, and for the overall summary.

Prior and concomitant therapies will also be presented in data listings.

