5.7 Concomitant Therapy

Except for excluded medications ([Section 5.8](#)), medications for symptoms and supportive management are permitted. During the study, if the use of any concomitant treatment becomes necessary (e.g., for treatment of an AE), the treatment must be recorded on the source document and eCRF, including the reason for treatment, name of the drug, dosage, route, and date of administration. All medications including prescription, over-the-counter (OTC), herbal, and other nutritional vitamins and/or supplements taken within 60 days of Day 1 will be recorded on the eCRF.

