6.4.5 Concomitant Medication Use

Concomitant treatment is permitted if the medication is not expected to interfere with the evaluation of safety or efficacy of the study drug. During the study, if the use of any concomitant treatment becomes necessary (e.g., for treatment or prophylaxis of an AE), the treatment must be recorded on the eCRF, including the reason for treatment, generic name of the drug, dosage, route, and date of administration. Restricted and prohibited concomitant medication use is presented in [Section 5.8](#).

The use of concomitant medications will be recorded from Day 1 through the end of the Treatment period or until the time of disease progression. Details of concomitant medication use should include the name, dose, route of administration, and indication.

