All concomitant medications and prior medications will be coded to therapeutic drug classes and generic drug names using the World Health Organization (WHO) Drug Classification. The incidence of prior and concomitant medication usage will be summarized by treatment arm, by therapeutic drug class, and generic drug names.

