### 7.2.2 Partial Dates for Concomitant Medication

For concomitant medications (CM) with incomplete dates, imputation will be used to convert to a complete date. Imputed dates will be used to determine Study Day.

Partial medication start dates will be imputed as follows:

- If year of the CM start date is missing, no date imputation will be made.
- If both day and month of the CM start date are missing but year is known, the day and month will be imputed with the day and month of the first study dose date if the year is equal to the year of first dose. Otherwise, the month and day is imputed as the first day of the year (01 Jan).
- If only day is missing, and if the year and month are equal to the first dose date, the day will be imputed as day of the first dose date. Otherwise, the day will be imputed as “01.”

Partial medication end dates will be imputed for non-ongoing medications as follows:

- If year of the CM end date is missing, no date imputation will be made.
- If both day and month of the CM end date are missing but year is known, the date of the last dose of study drug will be used as the end date of the medication. Otherwise, December 31 will be used as the end of the medication.
- If only day is missing, the date of last dose of study drug will be used as the end date of the medication. Otherwise, the last day of the month will be used as the end of the medication.

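### SAP 8.3.7 classifies medication by start date alone: a drug with a known earlier or missing start that continues on study counts as prior only, and a Day 1 start counts in both tables

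*SAP*

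**What the plan says.** SAP 8.3.7 gives one condition for each category. A concomitant drug "is any medication with start date on or after the initial dosing of study treatment". The other category has its own test, again resting on the start alone: a drug of that kind "is defined as any medication with start date on or before the first day of study treatment, or medication with start date missing". The two are then reported in separate tables: "The incidence of prior and concomitant medication usage will be summarized by treatment arm, by therapeutic drug class, and generic drug names on safety set".

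SAP 7.2.2 completes partial dates. A start with only the day missing, in the month and year of first dose, is handled so that "the day will be imputed as day of the first dose date". A start with day and month missing, in the year of first dose, takes the day and month of first dose. A start with no year is left as it is. End dates are also completed: "Partial medication end dates will be imputed for non-ongoing medications as follows".

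The protocol collects what a fuller definition would need. Section 5.7 has all medications "taken within 60 days of Day 1 will be recorded on the" eCRF. Section 6.4.5 describes concomitant medication by use: "The use of concomitant medications will be recorded from Day 1 through the end of the Treatment period". Section 7.8 repeats the planned summary ("The incidence of prior and concomitant medication usage will be summarized by treatment arm") but defines neither term. SAP section 9 makes the SAP govern where the two documents differ.

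**The concern.** A reader takes a concomitant medication table to show what subjects were taking while on study drug. Under SAP 8.3.7 it shows mainly what they newly started. Long-term medication carried into the trial appears only in the prior table, where it cannot be told apart from drugs stopped before first dose.

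This has some relevance here because CMB305 is meant to act by inducing an immune response. Protocol 4.3 and 5.8.2 leave room for some corticosteroid use: topical and inhaled products are allowed, and physiologic doses are possible with sponsor agreement. A subject who was on such a drug before Day 1 and stayed on it through dosing would be missing from the concomitant table for that drug. A comparison of on-study use between arms would then be incomplete.

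The Day 1 overlap is a smaller matter. The same record can enter both tables only because both definitions include that day.

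**Working it through.** There is no figure in the plan to reproduce. The check applies the rules to test records.

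**Inputs.** Let S be the start date and E the end date, with first dose on Day 1.

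- SAP 8.3.7: concomitant if S ≥ Day 1; prior if S ≤ Day 1 or S is missing.
- Use-based comparison rule: concomitant if S ≥ Day 1, or if S is earlier or missing and the drug is ongoing or E ≥ Day 1; prior if S < Day 1 or S is missing.

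| Test record | SAP 8.3.7 | Use-based rule |
|---|---|---|
| Start Day -30, end Day -5 | prior | prior |
| Start Day -30, continued to Day 100 | prior | prior and concomitant |
| Start Day -1, ongoing | prior | prior and concomitant |
| Start Day 1, end Day 20 | prior and concomitant | concomitant |
| Start Day 22, end Day 30 | concomitant | concomitant |
| Start wholly missing, ongoing | prior | prior and concomitant |
| Start day missing, in month of first dose (imputed to Day 1), ongoing | prior and concomitant | concomitant |

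Three of the seven records (the second, third and sixth) were taken on study but do not reach the concomitant table. Two (the fourth and seventh) enter both tables because Day 1 satisfies both conditions. These are constructed cases and say nothing about frequency.

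**Day 1 overlap.** One definition refers to the initial dosing and the other to the first day of treatment. If clock times were used, a drug started on Day 1 before the injection would be prior only, but one started after it would still be in both. The SAP mentions dates only.

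**Is it repaired elsewhere?** No. Protocol 7.8 has no definition, and no other section adds an end-date or ongoing condition. SAP 7.2.2 uses imputed dates to derive Study Day, but 8.3.7 makes no use of end dates.

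**What happens once end dates are used.** Read literally, SAP 7.2.2 sets an end date with only the day missing to the date of the last study dose, with no condition on month or year. The alternative it then offers, the last day of the month, has no stated trigger. Take a drug known to have stopped in the calendar month before first dose, day unknown. Its imputed end would be the last study dose date, so E ≥ Day 1 and the use-based rule would call it concomitant. If the last-dose date is used only when the known month and year match it, the imputed end is the last day of the earlier month, E < Day 1, and the drug stays prior only. The same gap exists for end dates with only the year known. An end date with no year is not imputed at all.

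**The case against.** The strongest reply is that little is lost. A drug started before Day 1 is properly a prior medication; the fault is only that it is not also counted as concomitant. It still appears by arm in the prior table and in the listings. No hypothesis test or analysis set depends on the classification. This stands, and it limits the point to a descriptive table.

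A reader might infer that the concomitant table would omit all long-term medication. The documents do not support that. Long-term drugs started on or after Day 1 are included, and some drugs that truly began earlier are included because SAP 7.2.2 moves their partial start date to first dose.

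A reader might also infer that use of prohibited immunosuppressants would be hidden. That is largely covered elsewhere. Protocol 4.3 (exclusion 5) and 5.8.1 bar these drugs in the 21 days before Day 1, and 5.8.2 bars them on study. A subject taking one would be a protocol deviation; SAP 8.1.2 lists all deviations and summarizes the reportable ones by type. One newly started on study meets the SAP definition of concomitant. The practical example is therefore permitted use.

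Finally, SAP 5.1.1.2 names the last concomitant medication among the sources for the last-known-alive date, so a reader might infer an effect on overall survival censoring. That date is the latest of many sources, including long-term follow-up and end-of-study contact, and the SAP does not tie it to the 8.3.7 classification.

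Whether a continuing drug should appear in one table or both is a matter of convention.

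**Conclusion.** The point holds in limited form. As written, the SAP leaves out of the concomitant table any drug taken on study whose start is known (or imputed) to precede first dose, or is wholly missing. It counts any start on, or imputed to, Day 1 in both tables. The concomitant table can therefore only under-state on-study use of continuing drugs. By how much cannot be said, because the documents give no counts.

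This rests on reading 8.3.7 literally at date level and on there being no definition elsewhere that overrides it. Primary endpoints, alpha, power and sample size are untouched. It is a minor correction, worth making because the required data are already collected.

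**What to change.** In SAP 8.3.7:

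- Define concomitant as any medication taken on or after first dose. That means a start on or after first dose, or an earlier or missing start with the drug ongoing or its end date on or after first dose.
- Define prior as any medication started before first dose. A Day 1 start is then not automatically in both tables, while a continuing drug may appear in both.
- Treat a missing start as prior as well, unless other information shows otherwise.

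In SAP 7.2.2:

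- Impute a partial end date to the last study dose date only when the known month and year (or the known year, if that is all there is) match that date. Otherwise use the last day of the known month or year.
- State how a medication with no end year is classified.

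The 7.2.2 change should go in together with the first; without it, the new definition would pull some drugs stopped before Day 1 into the concomitant table. The cost is a few SAP sentences and minor programming before database lock, with no new data collection.

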### **8.3.8 Analysis of Other Safety Variables**

Analyses for other safety variables will be performed based on the nature of the parameters and assessment schedule as needed.

A shift table for ECOG comparing the worst post baseline to baseline will be presented by treatment arm and overall.

